7.9 Intraocular Pressure

IOP will be measured according to routine clinical practice using Goldmann applanation tonometry or Tono-Pen in both eyes at all study visits. At the Baseline (Day 1) dosing visit, IOP must be performed prior to dilation and the IVT injection of study drug. A single measurement will be made to obtain a determination of the IOP at each study visit. Whether Goldmann applanation tonometry or Tono-Pen is used during the study, the Investigator's standard technique will be used throughout the study. In addition, all reasonable efforts will be made to have the same examiner obtain all IOP measurements for a given subject using the same instrument for screening and the subject follow-up assessments for each subject.

The Goldmann applanation tonometer or Tono-Pen instrument must be calibrated for accuracy before the first subject in the study at a given study center undergoes the first examination, and continue to be performed in accordance with the manufacturer's specifications until the last subject at the study center has exited the study. For detailed instructions regarding instrument calibration, refer to the calibration instructions supplied with the instrument.

7.10 Dilated Ophthalmoscopy

Dilated fundus examination of both eyes will be performed in all subjects by designated qualified study center personnel (i.e., an ophthalmologist). The following will be observed for the presence of abnormalities:

- Vitreous body
- Macula
- Peripheral retina
- Choroid
- Optic nerve

If any findings are abnormal, exact description of the findings should be specified and noted as either clinically or not clinically significant. All abnormal findings that are clinically significant and were not present at baseline, will be described and reported as AEs.

7.11 Spectral Domain – Optical Coherence Tomography

The SD-OCT imaging will be performed for both eyes to measure and assess cross-sectional images of the anatomic layers of the retina and to detect the presence of retinal fluid. Images will be obtained using a SD-OCT device by designated certified study center personnel. Preferably the same device will be used for screening and the subsequent follow-up assessments for each subject. For detailed instructions regarding collection of SD-OCT imaging, refer to the separately provided Image Acquisition Guidelines (IAG).

7.12 Intravitreal Depot Color Fundus Photography

CFP images will be taken on each subject's study eye to help identify the IVT GB-102 depot and the status of the visual axis. The initial images of the depot in the study eye, as well as the status of the visual axis should be obtained at baseline (Day 1) *after* the IVT injection and conducted through study completion at each visit for all subjects. Where available, Zeiss Clarus 500, Optos California Ultra-widefield or other specified Fundus Imaging systems should be used to collect these images.

The photographs may be used to document the general appearance and rate of bioabsorbability of the depot and to confirm that the depot is not interfering with the visual axis. For detailed instructions regarding collection of the IVT depot CFP imaging, refer to the separately provided guideline.

7.13 Postinjection Assessments

Following intravitreal injection of GB-102 at the Baseline (Day 1) visit, the subject should remain seated for approximately 15 minutes post-injection with minimal to no movement of the head (e.g., bending over, shaking head, laying down) and avoid significant eye movement.

During this 15 minute-time period, the injecting investigator/physician will assess postinjection safety using count fingers or hand motion vision. The injecting investigator/physician can conduct additional safety assessments (eg, additional IOP measurement and/or ophthalmoscopy), if needed, prior to the subject leaving the clinic. All subjects will receive a telephone call from the study center the following day to ensure there are no significant complaints or AEs.

8 ADVERSE EVENTS

Adverse events will be monitored continuously during the study from the time that the subject has provided written informed consent through the subject's last day of study participation. The following information will be collected for all AEs and recorded on the subject's source document and AE CRF:

- Event description (diagnosis preferred, if unknown, record the signs/symptoms)
- Onset and resolution dates
- Severity (intensity)
- Relationship to study drug or study procedure (causality) as determined by the assessing investigator
- Seriousness
- Expectedness
- Action taken with study drug
- Action taken with nondrug therapy
- Outcome

8.1 Definition of an Adverse Event

An AE is any untoward medical occurrence associated with the use of a drug in humans, whether or not considered drug-related.

An AE can therefore be:

- Any unfavorable and unintended medical diagnosis, sign, or symptom
- Any new undesirable medical occurrence or unfavorable or unintended change in a pre-existing condition that occurs during or after study treatment
- Vital sign or ophthalmic assessment that is assessed as clinically significant and different from baseline (eg, requiring discontinuation of study treatment, specific treatment, or a change in subject management); if possible, changes in laboratory results or changes in vital signs that meet the definition of an AE should be reported as a medical diagnosis rather than as the abnormal value (eg, "hypertension" rather than "blood pressure increased")

The following are special considerations when determining and reporting AEs:

- Whenever possible, the investigator should group signs or symptoms that constitute a single diagnosis under a single AE term (eg, “cough, rhinitis, and sneezing” might be grouped together as “upper respiratory tract infection”).
- Progression of neovascular AMD, including worsening of anticipated clinical signs or symptoms, which are collected as clinical efficacy variable and assessed as unequivocally associated with the disease progression and/or lack of efficacy, should NOT be reported as AEs unless disease progression is greater than anticipated in the natural course of the disease.
- A pre-existing condition is not considered an AE unless the condition worsens (increases in frequency, severity, or specificity) during or following study drug administration. Fluctuations in a pre-existing condition should be assessed by the investigator, and those that fall within the limits of expected fluctuations for the disease state (and are not assessed as worsening of the disease) should not be considered AEs. Any change assessed as clinically significant worsening of the disease from baseline must be documented as an AE.
- Elective surgery or routine diagnostic procedures are not considered AEs. However, an untoward medical event occurring during the prescheduled elective surgery or diagnostic procedure should be recorded as an AE.
- Death itself is not considered an AE; it is instead the outcome of an AE.

A treatment emergent adverse event (TEAE) is an AE with an onset anytime from when the subject has received study drug through 30 days after the study ends whether or not it is considered causally related to the study drug.

Note: AEs must be collected once informed consent has been obtained, regardless of whether or not the subject has been administered study drug.

8.1.1 Severity

Refer to [Appendix 18.2](#) and [Appendix 18.3](#) for definitions and assessment scales for ocular and nonocular/systemic AEs.

8.1.2 Expectedness

The expectedness of an AE should be determined based upon existing safety information about the investigational product using these explanations:

- *Unexpected*: an AE that is not listed in the IB or is not listed at the specificity or severity that has been observed.
- *Expected*: an AE that is listed in the IB at the specificity and severity that has been observed.

- *Not applicable*: an AE unrelated to the investigational product.

Adverse events that are mentioned in the IB as occurring with a class of products or as anticipated from the pharmacological/ mechanical (or other) properties of the product, but are not specifically mentioned as occurring with the particular product under investigation are to be considered unexpected.

The investigator should initially classify the expectedness of an AE, but the final classification is subject to the Medical Monitor's and Sponsor's determination.

8.2 Serious Adverse Event

All AEs will be assessed as either serious or nonserious. An SAE is any event that involves or results in any of the following outcomes:

- Death
- Life-threatening occurrence (ie, if in the view of the investigator or Sponsor, the event's occurrence placed the subject at risk of death at the time of the event; it does not refer to an event which hypothetically might have caused death if it were more severe)
- Requires in-patient hospitalization or prolongation of existing hospitalization (hospitalization for elective surgery for a pre-existing condition or for surgery planned before study entry is not considered an SAE)
- A persistent or significant disability/incapacity (permanent or substantial disruption of the subject's ability to perform normal life functions); this definition is not intended to include experiences of relatively minor or temporary medical significance
- Congenital anomaly/birth defect (an AE that occurs in the child or fetus of a subject exposed to study drug prior to conception or during pregnancy)

An important medical event or serious medical condition that does not meet any of the above criteria may be considered an SAE if, based upon appropriate medical judgment, it jeopardizes the subject or requires medical or surgical intervention to prevent one of the outcomes listed above. Examples of such medical events include allergic bronchospasm requiring intensive treatment in an emergency room or at home, blood dyscrasias, or convulsions that do not result in in-patient hospitalization, or the development of drug dependency or drug abuse.

8.3 Study Drug Causality

The assessing investigator will assess the relationship of the AE to the study drug or study procedure as either related or not related. The following should be taken into consideration when assessing AE causality:

- Positive temporal relationship to study drug, such as if the study drug was withdrawn and the AE resolved or the event recurred after re-introduction
- If there is a reasonable possibility that the AE is associated with an underlying or concomitant illness
- Possible association with previous or concomitant therapy
- No temporal relationship to the study drug and/or a more likely alternative etiology exists
- If the AE is directly related to study procedures

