8.4 Adverse Event Reporting Procedures

The occurrence of AEs should be sought by nonleading questioning of the subject at each scheduled or unscheduled study visit. At each visit, study personnel should ask the following question: “Have you had any problems since your last visit?” An AE may also be detected when volunteered by the subject during and between visits, or through physical examination or other assessments. All AEs (serious and nonserious) reported by the subject will be reviewed by a qualified physician participating in the study and must be recorded on the subject’s source documents and AE CRF.

All SAEs, whether or not related to study drug, must be reported to the Sponsor or Sponsor’s designated Pharmacovigilance contact immediately and must be submitted on an SAE report form within 24 hours after the investigator becomes aware of the event.

If an SAE occurs, the study center should immediately notify Graybug Vision email notification: [contact]. The project manager will notify the medical monitor and/or the Sponsor immediately (within 24 hours).

Alternatively, the investigator may contact the medical monitor directly:

Note that any SAEs that occur after the subject has provided written informed consent, but before administration of study drug and are considered related to a protocol procedure must also be reported to the Sponsor or Sponsor’s designated project manager within 24 hours after the investigator’s awareness of the event.

Investigators should not wait to receive additional information to fully document an SAE before reporting the event to the Sponsor or Sponsor’s designated project manager. If only limited information is initially available, follow-up reports are required. Additional relevant information

such as hospital records, laboratory test results, or autopsy reports should be provided as soon as these are available.

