8.5 Reporting Serious Adverse Events to Regulatory Agencies

An AE, whether serious or nonserious, is considered “unexpected” if the event is not reported in the clinical safety section of the reference document (eg, an IB or package insert) or if the event is of greater severity or frequency than is reported in the reference document.

Expedited reporting of SAEs is required for serious events that are both unexpected based on the reference document and considered related to the study drug (ie, the relationship cannot be ruled out). The Sponsor will determine which SAEs qualify for expedited reporting.

Reports of those SAEs that qualify for expedited reporting submitted to regulatory agencies in accordance with applicable local regulation (eg, 21 CFR 312.32).

Expedited reports will also be distributed to investigators. Upon receiving such notices, the investigator must immediately submit a copy of this information to the governing institutional review board (IRB) in accordance with the board’s guidelines and any applicable local regulations.

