- An important medical event or serious medical condition that does not meet any of the above criteria may be considered an SAE if, based upon appropriate medical judgment, it jeopardizes the subject or requires medical or surgical intervention to prevent one of the outcomes listed above. Examples of such medical events include allergic bronchospasm requiring intensive treatment in an emergency room or at home, blood dyscrasias, or convulsions that do not result in in-patient hospitalization, or the development of drug dependency or drug abuse.

An overall summary will be presented that includes the number of TEAEs and the number and percentage of subjects who experienced at least one TEAE, total and by cohort. This summary will also include breakdowns of TEAEs further categorized as ocular (study eye and non-study eye, separately), non-ocular, serious TEAEs, TEAEs by maximum severity, treatment-related TEAEs, and TEAEs leading to subject withdrawal.

Additional summaries of TEAEs will be provided showing the number and percentage of subjects who experienced at least one TEAE and total number of events. These summaries will be presented by SOC and PT. Non-ocular TEAEs will be summarized using discrete summary statistics and presented by cohort and total subjects at the subject and event level by SOC and PT. Ocular TEAEs will be similarly summarized at the subject level for study and non-study eyes separately. If a subject has multiple TEAEs coded to the same PT within same SOC, that PT will only be reported once. As with the PT, if a subject reports multiple conditions within the same SOC, that SOC will only be reported once at the subject level. In the summary, SOCs are listed in order of decreasing frequency for total subjects. PTs are listed in order of decreasing frequency within each SOC for total subjects. The occurrence of non-ocular and ocular TEAEs will also be tabulated by SOC and PT for the following: maximal severity and suspected relationship to study drug.

Separate summaries will be provided for the following categories of AEs:

- Ocular TEAEs in the study eye
- Ocular TEAEs in the non-study eye
- Non-ocular TEAEs
- Treatment-related ocular TEAEs in the study eye
- Treatment-related ocular TEAEs in the non-study eye
- Treatment-related non-ocular TEAEs
- Ocular serious TEAEs in the study eye
- Ocular Serious TEAEs in the non-study eye
- Non-ocular serious TEAEs
- Treatment-related ocular serious TEAEs in the study eye

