- Treatment-related ocular serious TEAEs in the non-study eye
- Treatment-related non-ocular TEAEs
- Ocular TEAEs by maximal severity in the study eye
- Ocular TEAEs by maximal severity in the non-study eye
- Non-ocular TEAEs by maximal severity
- TEAEs leading to premature study discontinuation (if applicable)

The NCI-CTCAE (National Cancer Institute – Common Terminology Criteria for Adverse Events) (version 4.03) is a descriptive terminology that will be used to grade the severity of non-ocular AEs reported in this

study. The NCI-CTCAE displays Grades 1 through 5 with unique clinical descriptions of severity for each AE based on this general guideline:

- Grade 1: Mild; asymptomatic or mild symptoms; clinical or diagnostic observation only; intervention not indicated
- Grade 2: Moderate; minimal, local, or noninvasive intervention indicated; limiting age-appropriate instrumental activities of daily living (ADL)\*
- Grade 3: Severe or medically significant but not immediately life-threatening; hospitalization or prolongation of hospitalization indicated; disabling; limited self-care ADL\*\*
- Grade 4: Life-threatening consequences; urgent intervention indicated
- Grade 5: Death related to an AE

A semicolon indicates “or” within the above descriptions. A single dash (–) can be used to indicate that a grade is not available. Not all grades are appropriate for all AEs. Therefore, some AEs are listed with fewer than 5 options for grade selection.

- \* Instrumental ADL refer to preparing meals, shopping for groceries or clothes, using the telephone, managing money, etc.
- \*\* Self-care ADL refer to bathing, dressing and undressing, feeding self, using the toilet, taking medications, and not being bedridden.

The severity grading of ocular AEs reported in this study will not employ the NCI-CTCAE criteria defined above but will be graded as described here. Severity of an ocular AE is defined as a qualitative assessment of the degree of intensity of an AE as determined by the Investigator or reported to him/her by the subject. The assessment of severity is made irrespective of relationship to the study drug or seriousness of the event and should be evaluated according to the following scale:

- *Mild*: Event is noticeable to the subject but is easily tolerated and does not interfere with the subject's daily activities.
- *Moderate*: Event is bothersome, possibly requiring additional therapy, and may interfere with the subject's daily activities.

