- *Severe*: Event is intolerable, necessitates additional therapy or alteration of therapy, and interferes with the subject's daily activities.

Summaries of TEAEs by maximal severity will be provided showing the number and percentage of subjects who experienced at least one TEAE and total number of events. These summaries will be presented by SOC and PT. Non-ocular TEAEs will be summarized using discrete summary statistics and presented by cohort and total subjects at the subject and event level by SOC and PT. Ocular TEAEs will be similarly summarized at the subject level for study and non-study eyes separately.

The relationship of each AE to the study drug should be determined by the Investigator using these explanations:

- *Related*: A reasonable possibility exists that the study drug caused the AE.
- *Not Related*: A reasonable possibility does not exist that the study drug caused the AE.

Summaries of all ocular and non-ocular TEAEs, TEAEs by maximal severity, TEAES related to the study drug, and serious TEAEs will also be tabulated by study site for each cohort and total subjects. All ocular AEs occurred in study eye and non-study eye will be summarized separately.

All TEAEs will be presented in a subject listing. The TEAEs leading to study treatment discontinuation will be listed separately. In addition, all serious AEs will be presented in a separate listing.

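### If the adverse event form takes one causality answer for drug and procedure together, as Protocol 8.3 suggests, the SAP's product-related tables can include events due only to the injection procedure

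*Protocol*

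**What the plan says.** Protocol 8 lists the items collected for every adverse event. One of them is "Relationship to study drug or study procedure (causality) as determined by the assessing investigator". Protocol 8.3, headed Study Drug Causality, gives the response scale: "The assessing investigator will assess the relationship of the AE to the study drug or study procedure as either related or not related". It then lists considerations for the assessor. The last is whether the event is a direct result of study procedures, and the section does not say whether that counts towards related or not related.

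Elsewhere the protocol treats drug and procedure as different questions:
- Protocol 8.4 names procedure-relatedness separately, but only for serious events that occur "before administration of study drug and are considered related to a protocol procedure must also be reported".
- Protocol 8.5 ties expedited reporting to events "considered related to the study drug (ie, the relationship cannot be ruled out".
- Protocol 8.1.2 has a Not applicable answer to the Expectedness item, for "an AE unrelated to the investigational product".

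SAP 13.1 defines Related as: "A reasonable possibility exists that the study drug caused the AE". The procedure is not mentioned. The overall summary is to include "TEAEs by maximum severity, treatment-related TEAEs, and TEAEs leading to subject withdrawal". SAP 15 then lists nine tables whose titles attribute the events to the investigational product: three for the study eye, three for the non-study eye and three non-ocular. No table or listing title in the SAP refers to procedure-related events.

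**The concern.** The treatment-related tables are where a reader looks for the risk of GB-102 itself, as distinct from the risk of any intravitreal injection. Every subject is injected on Day 1 and there is no control arm, so no comparison removes the contribution of the injection.

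The distinction matters for this product. In the single-dose rabbit study (Protocol 1.5.1.3) the lens opacities were put down to the injected volume. In the repeat-dose rabbit study the opacities were attributed to the test article. The nonclinical programme separated these causes; the planned clinical tables, fed by a joint answer, would not.

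The SAP cannot repair this afterwards. Its introduction lets it supersede the protocol's statistical methods, but no analysis method can split an answer that investigators gave jointly.

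**Working it through.** The documents give no figure to reproduce on this point. The check compares the passages and then scales the effect.

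**Step 1. What is recorded against what is tabulated**

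| Place | Subject of the causality judgement |
|---|---|
| Protocol 8, list of items | drug or procedure, one item |
| Protocol 8.3, response scale | drug or procedure, one related/not-related answer |
| Protocol 8.3, heading | drug |
| Protocol 8.3, last consideration | procedure, direction not stated |
| SAP 13.1, definitions | drug only |
| SAP 15, relatedness tables | investigational product only |

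On the natural reading of Protocol 8 and 8.3, an event due only to the procedure is answered related. The SAP's definition would exclude that event, but if the data hold one combined answer, the SAP's tables include it.

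**Step 2. Which outputs are exposed**

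Tables titled by investigational product:
- study eye: 14.3.3.1, 14.3.5.1, 14.3.15.1
- non-study eye: 14.3.3.2, 14.3.5.2, 14.3.15.2
- non-ocular: 14.3.3.3, 14.3.5.3, 14.3.15.3

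That makes 3 + 3 + 3 = 9. GB-102 is injected only into the study eye, so the main exposure is 14.3.3.1 (all related ocular events) and 14.3.5.1 (serious ones). Table 14.3.15.1 repeats 14.3.3.1 by site. The treatment-related row of Table 14.3.1.1 is also exposed, and that table is in the topline delivery. The other six tables are less exposed, though procedures such as tonometry and dilation are done in both eyes.

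**Step 3. Size per affected subject**

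Inputs: 10 subjects planned per dose and 20 in total (Protocol 3.1 and synopsis; SAP 4.1). Let k be the number of subjects in one dose group whose only related event in a given row is procedural.

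- Shift in that dose group: 100 × k / 10 = 10k percentage points.
- Shift in the total column: 100 × k / 20 = 5k percentage points.

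The documents do not give k. As an assumed range for scale only:

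| k | Dose group | Total |
|---|---|---|
| 0 | 0 | 0 |
| 1 | 10 | 5 |
| 2 | 20 | 10 |
| 3 | 30 | 15 |

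**Step 4. What does not move**

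A treatment-emergent event is defined in Protocol 8.1 and SAP 13.1 by onset after dosing, whatever its cause. The all-cause counts, and so the primary endpoint counts, change by 0.

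**The case against.** The strongest reply is that the adverse event form is not in the documents. It may already hold separate drug and procedure fields. SAP 13.1 speaks of the relationship of each event to the study drug, which would fit a drug-specific field. The heading of Protocol 8.3 and its last consideration can also be read together as a drug-only judgement, with a procedural cause counting against. This stands, and it makes the finding conditional. It does not remove the conflict in the text: the operative sentence of 8.3 and the item in Protocol 8 both name the procedure, and the SAP definition does not.

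Second, Protocol 9.5.1 promises treatment-related summaries and never a procedure-related count. That is correct. The missing count breaks no commitment; the inconsistency lies in the definition and the titles.

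Third, other information helps with individual cases: onset dates, the check within 15 minutes of injection and the next-day call. Both doses use the same volume and needle, so a dose difference carries some information about the drug, although allocation is by consecutive enrolment rather than randomised. The SAP also plans to list all study data and includes a listing of all adverse events. Its columns are not shown, but about 20 subjects could be reviewed by hand if Expectedness and causality appear there. All this helps case review, but none of it puts a product-only count in the planned tables.

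A reader might infer that the expedited-reporting rule in Protocol 8.5 fails. The documents do not show that, because the sponsor decides which serious events qualify.

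**Conclusion.** The protocol and SAP state different causality questions. If the form follows the protocol wording and stores one answer, events due only to the injection procedure can appear under product-related titles. Each affected subject then moves the related rate by 10 points in a dose group of 10 and by 5 points in all 20. The conclusion rests on two things the documents do not settle: that the form has a single combined field, and that at least one subject has a procedural event as the only related event in the row.

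Three stronger readings are tempting and not supported:
- The primary safety result is not distorted, because all-cause counts are independent of the causality answer.
- Product risk is not hidden; the error runs towards overstating it.
- No probability that the tables are affected can be given, because the documents contain no rate of procedure-only events.

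No hypothesis is tested, so no formal inference is at stake. The point should be corrected because safety is the primary objective of an uncontrolled study and the remedy is small.

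**What to change.** Preferred change:
- In Protocol 8 and 8.3, and on the adverse event form, record two answers: related to GB-102, and related to a study procedure. Within the second, identify the Day 1 GB-102 injection separately from other study procedures and from rescue injections, which go into the same eye.
- In SAP 13.1, state that only the first answer feeds the treatment-related row of Table 14.3.1.1 and every table titled by investigational product.
- Show study-eye procedure-related counts beside Tables 14.3.3.1 and 14.3.5.1.

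If the form already has both fields, only the SAP sentence and the added counts are needed.

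If the form cannot change, align the SAP 13.1 definition with the combined answer and retitle the tables to say that they cover drug or procedure. In the adverse event listing, flag study-eye events answered related with Expectedness marked Not applicable. This separates the causes only partly, but it removes the misleading label.

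Cost: the preferred change takes one extra judgement per event, added form fields and a small extra tabulation. An event can be related to both drug and procedure, so the two counts can overlap and will not add to a total; a footnote should say so. The fallback costs one definition, new titles and a listing flag.
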